3. OBJECTIVES

3.1 PRIMARY

The primary objective is:

- To evaluate the dose required to achieve steady-state FIX levels >12% of a SC prophylaxis treatment regimen of CB2679d, in adult subjects with hemophilia B.

3.2 SECONDARY

The secondary objectives are:

- To determine the PK of a SC regimen of CB2679d.
- To determine the PD of a SC regimen of CB2679d.
- To evaluate the levels of thrombogenicity markers of a SC regimen of CB2679d.
- To evaluate for evidence of the development of antibodies to CB2679d and to determine if these are neutralizing antibodies.
- To monitor and evaluate safety parameters of a SC regimen of CB2679d.

Dalcinonacog alfa_DLZ-201 VERSION 2.0, Amendment 1

4. STUDY DESIGN

4.1 OVERALL DESIGN

This is a single-center, open-label Phase 2b study designed to evaluate the PK, PD, efficacy and safety of SC prophylaxis treatment regimens with CB2679d in adult subjects with hemophilia B. It is an open-label study, so subjects and members of the clinical study team will not be blinded to treatment. It is estimated that it will take approximately 6 months from when the study opens enrollment until completion of last patient last visit. The study will enroll a total of 6 adult male subjects with severe congenital hemophilia B. Participants will be given SC prophylaxis CB2679d regimens over a 4-week period, with the goal to achieve steady-state levels above 12% FIX activity when dosed daily.

Each subject will participate for approximately 4-weeks (28 days) of SC CB2679d drug administrations:

Treatment: Day 1 to Day 28: Each participant will receive an IV loading dose of 50 IU/kg followed 35 ± 5 minutes later by a SC dose of 100 IU/kg. **Daily** SC doses of 100 IU/kg will be administered until Day 28 (28 total SC doses). On day 1, PK, PD, and safety assessments will be done at pre-IV dose and repeated 35 (± 5) minutes later prior to the SC dose. Subsequent PK, PD and safety assessments will be performed pre-dose on days 2, 3, 7, 14, 21 and 28.

Washout Period

PK, PD, and safety assessments will be done on Days 29, 30, 31, 32 and 33. Daily FIX activity levels will be measured, unless FIX activity level is known to be < 5% as measured by local laboratory.

An End of Study visit will occur 30 days (± 2 days) after the last dose of study drug.

Subjects will sign an ICF at the Screening Visit, prior to any study procedures. Eligibility to participate in the study will be determined by inclusion and exclusion criteria from medical history, hemophilia history, laboratory investigations and ECG. The screening period duration may be up to 4 weeks.

At enrollment, subjects will receive training and diary entry of self-administered investigational drug administration & injection site assessment, bleeding episodes & treatment, evaluation & entry of AEs.

Treatment of a spontaneous or traumatic bleeding episode: Subjects will use their current prescribed treatment regimen for any spontaneous or traumatic bleed that occurs while on study drug. If treatment for a spontaneous or traumatic bleeding episode is needed, then subjects will contact the clinical

Dalcinonacog alfa_DLZ-201 VERSION 2.0, Amendment 1

investigative team immediately to report the event, treatment dose administered, and determine follow-up plans for that event including whether to arrange for a blood specimen to be drawn (if feasible) before further administration of either study drug or the current prescribed treatment regimen used. Decision whether to continue daily study drug administration will also be determined by the clinical study team after discussion with the Sponsor.

Dose interruption: SC study drug injections will be interrupted if any of the following occurs: a thrombotic event; clinical evidence of inhibitor formation; or laboratory results suggesting a high titer antibody may be developing; trough activity levels >80% where subsequent dosing will be determined in consultation with the sponsor.

Surgery: If there is an urgent need for a surgical procedure or an event requiring extended (>48 hours) hospitalization, a FIX activity level will be urgently obtained and measured prior to the event, and the PI will confer with the Sponsor Medical representative regarding the need for any additional treatment and whether study drug requires interruption.

Measurements:

PK, PD, and safety assessments: FIX activity levels, as well as fibrinogen, D-dimer, F1+2, and TAT. PT and aPTT will be measured at screening and end of study visit only. Genotype testing will be performed at screening.

Immunogenicity assays: Specimens for immunogenicity testing (antibody to CB2679d, BeneFIX®, and neutralizing activity) will be drawn at screening, pre-dose on days 7, 14, 21, 28 and end of study.

If the FIX activity level decreases unexpectedly by more than 25%, ie, IU/dL, as measured by the central or local lab, FIX activity levels will be drawn for analysis within 24 hours and immediately sent to the central laboratory. Specimens for fibrinogen, D-dimer, F1+2, and TAT and immunogenicity testing will also be drawn.

4.2 END OF STUDY DEFINITION

The duration of treatment for each subject is approximately 4 weeks (28 days).

Up to 4 weeks for screening period; SC prophylaxis treatment regimens over a 4-week period with the goal to achieve steady-state levels above 12% FIX activity when dosed daily.

Dalcinonacog alfa_DLZ-201 VERSION 2.0, Amendment 1

Where interruptions to study drug dosing days occur, study duration may be extended to incorporate full dosing schedule.

The end of study visit will be 30 days \pm 2 days after the last dose of study drug treatment.

Dalcinonacog alfa_DLZ-201 VERSION 2.0, Amendment 1

5. STUDY POPULATION

5.1 INCLUSION CRITERIA

An individual must meet all of the following criteria to be eligible to participate in this study:

1. Confirmed diagnosis of severe (<2%) congenital hemophilia B.
2. Male, age 18 or older.
3. Agreement to use highly effective birth control throughout the study.
4. Affirmation of informed consent with signature confirmation before any trial-related activities. (Trial related activities are any procedure that would not have been performed during normal clinical management of the subject).
5. Stated willingness to comply with all study procedures and availability for the duration of the study.

5.2 EXCLUSION CRITERIA

An individual who meets any of the following criteria will be excluded from participation in this study:

1. Patients with a history or a family history of FIX inhibitors.
2. Positive antibody to FIX detected by central laboratory at screening.
3. Previous participation in and subsequent treatment in a clinical trial within the previous 30 days or 3-half-lives, whichever is longer, or absence of clinical effect.
4. History of clinically relevant coagulation disorders other than congenital hemophilia B including Factor V Leiden or other identified activated Protein C resistance.
5. Platelet count <100,000 based on screening laboratory assessments.
6. Advanced atherosclerotic disease (ie, known history of CAD, ischemic stroke, etc.), or known DVT or considered to be at a high risk of VTE as judged by the Investigator.
7. Known or suspected allergy to trial product or related products.
8. Known absolute CD4 count <200 cells/ μ L.
9. Receiving IMT.
10. Compromised hepatic or renal function:
 - o ALT and AST levels \geq 5 x ULN
 - o TBIL \geq 2 mg/dL ($>35 \mu$ mol /L) unless there is a known history of GS
 - o Serum albumin \leq LLN
 - o Cr level $>1.25 \times$ ULN

Dalcinonacog alfa_DLZ-201 VERSION 2.0, Amendment 1

11. Inability or medical, psychosocial, or familial issues that might prevent full participation and cooperation with the procedures and requirements of the clinical trial as determined by the potential subject and physician investigator.
12. Factor IX gene mutation 128G>A.

5.3 LIFESTYLE CONSIDERATIONS

There are no specific lifestyle considerations.

5.4 SCREEN FAILURES

An individual who does not meet the criteria for participation in this trial (screen failure) because of an out of range laboratory parameter may be rescreened.

Dalcinonacog alfa_DLZ-201 VERSION 2.0, Amendment 1

6. STUDY INTERVENTION

6.1 STUDY INTERVENTION(S) ADMINISTRATION

6.1.1 Study Intervention Description

Description and Composition of the Drug Product

Recombinant Factor IX variant; CB2679d, formerly known as ISU304, will be provided as a powder for injection, at a 2.0 mg/vial dosage strength. The drug product is supplied in a 5-mL vial that is sealed with a 20mm lyophile stopper and 20mm aluminum over-seal. CB2679d is supplied in vials which contain excipients (stabilizer, buffer, etc.) and packaged in a lyophilized form. Before lyophilization, each vial contains 1.42 mg/mL of CB2679d drug substance is filled with 1.4 mL of formulation buffer. The lyophilized drug product will be reconstituted for SC injection.

6.1.2 Dosing and Administration

This is an open-label study. Each subject will receive the study drug:

CB2679d loading dose of 50 IU/kg IV, followed 35 ± 5 minutes later with a 100 IU/kg, with SC administration daily until Day 28 (total 1 IV dose and 28 SC doses).

6.1.2.1 Guidelines for Treatment Interruption

CB2679d SC study injections will be interrupted, as needed, when:

- A surgical procedure is needed
- There is a medical event requiring extended (>48 hours) hospitalization
- If there is a thrombotic event
- If there is clinical evidence of inhibitor formation
- If there are laboratory results suggesting an antibody may be developing

CB2679d SC study injections may be interrupted, as needed, when:

- A spontaneous bleeding event occurs
- A traumatic bleeding event occurs

Dalcinonacog alfa_DLZ-201 VERSION 2.0, Amendment 1

Subjects will use their current treatment regimen for any spontaneous or traumatic bleed that occurs while on study. A spontaneous bleeding episode is defined as one that is precipitated by normal activities of daily living (ADL). If treatment for a spontaneous or traumatic bleeding episode is needed, then subjects will contact the clinical investigative team immediately to report the event; treatment dose administered; and determine follow-up plans for that event, including to arrange for a blood specimen to be drawn (if feasible). This information will also be recorded in the subjects' diary.

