Treatment of a spontaneous or traumatic bleeding episode: Subjects will use their current prescribed treatment regimen for any spontaneous or traumatic bleed that occurs while on study drug. If treatment for a spontaneous or traumatic bleeding episode is needed, then subjects will contact the clinical investigative team immediately to report the event, treatment dose administered, and determine follow-up plans for that event including whether to arrange for a blood specimen to be drawn (if feasible) before further administration of either study drug or the current prescribed treatment regimen used. Decision whether to continue daily study drug administration will also be determined by the clinical study team after discussion with the Sponsor.

Dose interruption: SC study drug injections will be interrupted if any of the following occurs: a thrombotic event; clinical evidence of inhibitor formation; or laboratory results suggesting a high titer antibody may be developing; trough activity levels >80% where subsequent dosing will be determined in consultation with the Sponsor.

Surgery: If there is an urgent need for a surgical procedure or an event requiring extended (>48 hours) hospitalization, a FIX activity level will be urgently obtained and measured, and the PI will confer with the Sponsor Medical representative regarding the need for any additional treatment and whether study drug requires interruption.

Measurements:

- **PK, PD, and safety assessments:** FIX activity levels, as well as fibrinogen, D-dimer, prothrombin fragment 1+2 (F1+2), and thrombin-antithrombin complexes (TAT). Prothrombin time and activated partial thromboplastin time (aPTT) will be measured at screening and end of study visit only. Genotype testing will be performed at screening.
- **Immunogenicity assays:** Specimens for immunogenicity testing (antibody to CB2679d, BeneFIX®, and neutralizing activity) will be drawn at screening, pre-dose on days 7, 14, 21, 28 and end of study.

If the FIX activity level decreases unexpectedly by more than 25%, ie, IU/dL, as measured by central laboratory, FIX activity levels will be drawn for analysis within 24 hours and immediately sent to the central laboratory. Specimens for fibrinogen, D-dimer, F1+2, and TAT and immunogenicity testing will also be drawn.

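### The current protocol gives two different lists of triggers for interrupting study drug, and nothing says which list governs

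*Protocol*

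**What the plan says.** All references are to the current protocol (version 2.0, Amendment 1) and the SAP.

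Protocol 4.1 (Overall Design) states a mandatory rule: "SC study drug injections will be interrupted if any of the following occurs: a thrombotic event; clinical evidence of inhibitor formation". The list then continues: "laboratory results suggesting a high titer antibody may be developing; trough activity levels >80% where subsequent dosing will be determined in consultation with the sponsor". The Synopsis (1.1) and SAP 3.3 (Brief Description) repeat the same four triggers; the SAP also limits the antibody item to "laboratory results suggesting a high titer antibody may be developing".

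Protocol 6.1.2.1 (Guidelines for Treatment Interruption) opens differently: "CB2679d SC study injections will be interrupted, as needed, when". Its list contains surgery, a medical event with more than 48 hours in hospital, a thrombotic event, clinical evidence of an inhibitor, and finally "If there are laboratory results suggesting an antibody may be developing". Factor IX trough activity does not appear.

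The two sections also part on surgery. In 6.1.2.1 the item reads "A surgical procedure is needed" and sits among the interruption triggers. In 4.1, urgent surgery or a hospital stay over 48 hours leads to a conversation between the investigator and the sponsor "regarding the need for any additional treatment and whether study drug requires interruption".

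**The concern.** Both texts govern the same act, yet they differ in which events count and in how binding the instruction is. Neither refers to the other, and no statement of precedence was found.

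The antibody item carries the most weight. Protocol 8.4.7 makes an immune response with antibody formation an adverse event of special interest. Protocol 2.2.2 reports that both subjects in cohort 6 of the preceding study, who had intravenous plus subcutaneous dosing as here, developed neutralizing antibodies. Samples for immunogenicity are drawn before dosing on Days 7, 14, 21 and 28, so a positive result can arrive while the subject is injecting himself daily. What happens next depends on the section consulted. Even a site that took 4.1 as governing could not apply it in a reproducible way, because the boundary of high titer is not stated.

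At stake are consistent safety handling across subjects and staff, and a clear basis for deciding whether an interruption, or its absence, is a protocol deviation.

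**Working it through.** There is no planned figure to reproduce. The check is a comparison of the lists. Bleeding episodes are left out because both sections leave them to judgement.

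| Topic | Synopsis 1.1, Protocol 4.1, SAP 3.3 | Protocol 6.1.2.1 | Same event? |
|---|---|---|---|
| Thrombotic event | Trigger | Trigger | Yes |
| Clinical evidence of an inhibitor | Trigger | Trigger | Yes |
| Laboratory suspicion of an antibody | Trigger if high titer | Trigger, no titer condition | No |
| Trough activity above 80% | Trigger | Not listed | No |
| Surgery | Investigator and sponsor discuss | Trigger | No |
| Hospital stay over 48 hours | Investigator and sponsor discuss | Trigger | No |
| Force of the instruction | Will be interrupted if any one occurs | Will be interrupted, as needed | No |

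Of the six topics, 2 agree and 6 − 2 = 4 differ. The last row is a further difference that touches even the two shared triggers.

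Applying the rules to particular subjects:

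1. Laboratory suspicion of an antibody that is not high titer, no clinical inhibitor, trough at or below 80%: a trigger in 6.1.2.1 and not in 1.1, 4.1 or SAP 3.3.
2. Trough above 80%, no antibody: a trigger in 1.1, 4.1 and SAP 3.3 and not in 6.1.2.1.
3. Thrombotic event or clinical inhibitor: a trigger everywhere, mandatory in one text and as needed in the other.
4. Surgery or more than 48 hours in hospital: a listed trigger in 6.1.2.1; an open question for discussion in 4.1.

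Definition of high titer: no value was found in either document. SAP 11.8 lists the titer for positive samples but sets no cut-off. The qualifier is also used unevenly for the endpoint: it is present in Protocol 9.1 and absent from Protocol 9.4.3 and SAP 4.2.

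The mismatch is not produced by setting a superseded text against a current one. All the passages compared are in force.

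**The case against.** The case for leaving this alone is that the texts can be read together. Section 6.1.2.1 is headed as guidelines, its as-needed wording leaves discretion, and neither list claims to be exhaustive, so a site could honour both. The trial has one center, bound by the whole protocol, and the trough rule appears in two of its sections. Much of this stands: different handling is possible, not certain. It does not remove the conflict, because an any-one-of rule in one section and a discretionary rule in another cannot both describe the intended instruction.

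The prior experience also needs its context. Protocol 2.2.2 says that the antibody was transient in one of the two subjects, and that a 3-month gap between cohorts was judged the most likely cause. No titers are given, so these cases do not show how likely a low-titer finding is here. A trough above 80% may be less likely still, since cohort 6 levels are reported only as rising above 30%.

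A reader might infer three stronger points that the documents do not support.

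- *That 4.1 acts only when a high-titer antibody and a high trough occur together.* They are separate items on an any-of list, which also shares two triggers with 6.1.2.1.
- *That a subject would be taken off treatment under one section and kept on under the other.* Both sections concern interruption, and Protocol 1.1 and 4.2 allow the study to be extended so that the full dosing schedule is given. An interrupted subject may therefore still complete the 21 days of dosing on which replacement turns, and still give late troughs.
- *That the primary result moves by 1/6 = 16.7 percentage points.* That is the weight of any one of six subjects, and no route to a changed result is shown. The first scheduled on-treatment antibody sample is on Day 7. By then factor IX has been sampled twice on Day 1 and once each on Days 2, 3 and 7, which is 2 + 3 = 5 time points against the four required for the PK population. The Day 2, 3 and 7 values also supply the 3 of 6 troughs required by SAP 9.4. SAP 8.1 counts subjects above 12% during the treatment period, so a value already recorded would usually still count. Limits on this rebuttal: assay turnaround is not stated, an unexpected fall in factor IX can prompt earlier sampling, and the steady-state assessment could lose late troughs.

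**Conclusion.** The point holds as an inconsistency in a safety rule. The protocol has two interruption lists that differ on four of six topics and in how binding they are, it uses an undefined term in one of them, and it does not say which prevails. Subjects in cases 1, 2 and 4 above could be handled differently depending on the section followed.

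The size is given by those differences in the text, not by a shift in an estimate. No probability can be attached to any of the cases from the documents, and no effect on the primary endpoint is claimed. The conclusion rests on reading the sections as written and on finding no cross-reference or order of precedence between them. It should be corrected, and it does not call the design or the analysis into question.

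**What to change.** Reconcile the Synopsis (1.1), Protocol 4.1, Protocol 6.1.2.1 and SAP 3.3 into one list of interruption triggers, held in one section and cross-referenced from the others. The list should state:

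- whether titer matters for the antibody trigger and, if it does, how high titer is defined;
- whether the trough trigger applies;
- how surgery and hospital stays over 48 hours are handled;
- whether interruption is mandatory or discretionary for each item.

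Which clinical rule to adopt is for the sponsor to decide; this review takes no position on it. The cost is amendment wording and a matching edit to SAP 3.3, with no added visits, samples or procedures.

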6.2 PREPARATION/HANDLING/STORAGE/ACCOUNTABILITY

6.2.1 Acquisition and Accountability

Upon receipt of the CB2679d shipment, the pharmacist, or a designee, will conduct an inventory and return an acknowledgement that all IP was received refrigerated and undamaged, thereby maintaining the Good Manufacturing Practice (GMP) status of the product during shipment.

All used and unused investigational product (IP) must be returned by the subject to the study site. Subjects must return all IP packages and vials (including used, empty, and unused vials) for reconciliation of IP.

The investigator, or approved representative (eg, pharmacist) must maintain adequate records documenting the receipt, use, loss, or other disposition of the IP. The sponsor will supply drug accountability forms to be used in this study.

The sponsor or designee will arrange for the return of unused IP. The IP destruction procedure for used vials is to be decided locally to comply with local regulations and procedures.

Drug accountability will be reviewed by the monitor during routine monitoring visits. No IP can be destroyed or returned until the study monitor has reconciled all vials of IP.

6.2.2 Product Storage and Stability

The investigator, or an approved representative, eg, pharmacist, will ensure that all IPs are stored in a secured area with controlled access under recommended storage conditions and in accordance with applicable regulatory requirements. The IP and its storage and preparation requirements will be provided by the Sponsor, or designee.

Dalcinonacog alfa_DLZ-201 VERSION 2.0, Amendment 1

IP should be stored in its original container and in accordance with the drug label. The Sponsor will provide the Investigator with packaged IP in accordance with specific country label requirements.

Site systems must be capable of measuring and documenting (for example, via a log), at a minimum, daily minimum and maximum temperatures for all site storage locations (as applicable, including frozen, refrigerated and/or room temperature products). This should be captured from the time of IP receipt throughout study. Even for continuous monitoring systems, a log or site procedure which ensures active daily evaluation for excursions should be available. The operation of the temperature monitoring device and storage unit (for example, refrigerator), as applicable, should be regularly inspected to ensure it is maintained in working order.

Any excursions from the product storage conditions should be reported upon discovery. The site should actively pursue options for returning the product to appropriate storage conditions, as soon as possible. Deviations from the storage requirements, including any actions taken, must be documented and reported to the Sponsor, or designee.

Once an excursion is identified, the IP must be quarantined and not used until the Sponsor, or designee, provides documentation of permission to use the IP. Specific details regarding information the site should report for each excursion will be provided to the site.

Receipt of materials, door opening and closing, and other routine handling operations where the product(s) are briefly out of labeled temperature range are not considered excursions. Site staff will instruct subjects on the storage requirements for take home medications including how to report temperature excursions.

